Evaluation of AI Cost Prediction Model to Enroll Patients in Complex Care Management Program

Analysis Plan

ID: IRB-24-0848

IRB Approved 6/12/2024

NCT ID: Not yet assigned

Document Updated March 31, 2025

Primary Outcome

Days alive and out of hospital (DAOH) at 120 days from randomization

Secondary Outcomes

- Days alive and out of hospital (DAOH) at 30 days from randomization
- Days alive and out of hospital (DAOH) at 90 days from randomization
- Days alive and out of hospital (DAOH) at 10 months from randomization
- Total healthcare expenditures at 10 months from randomization
- All-cause hospitalizations at 10 months from randomization
- All-cause emergency department visits at 10 months from randomization
- All-cause mortality at 10 months from randomization
- Ambulatory contact days out of home (days with a primary care or specialty care office visit, test, imaging, procedure, or treatment)

Exploratory Outcomes

- Cost prediction model performance over 22 months, as measured by area under the receiver operating characteristic curve. Observed healthcare expenditures for each month's control cohort will be measured over the subsequent 12 months after randomization (ie, 10 months of enrollment + 12 months of follow-up= 22 months), and compared to model-predicted healthcare expenditures. This analysis will only be conducted in the control group, as the intervention is designed to affect healthcare expenditures in the treatment group.
- Protocol fidelity over the 10 months of enrollment, measured by the proportion of patients randomized to the intervention who enroll in the complex care management program, and the proportion of patients randomized to the control who do not enroll in the complex care management program.
- Avoidable hospitalizations, defined as hospitalizations that could have been avoided through timely access to ambulatory care.
- Avoidable emergency department visits, defined as emergency department visits that could have been avoided through timely access to ambulatory care.

Analysis plan

The investigators will compare the outcomes between the intervention and control arms with Poisson regression using arm assignment as the primary model term. Regressions will control for age, sex, race/ethnicity, and each prior baseline outcome (e.g., for the DAOH-120 primary outcome, model will control for DAOH in the 120 days prior to randomization).

The randomization will be balanced on the primary outcome.

Power

The cost prediction model will identify approximately 500 patients each month, who will undergo a 1:1 randomization stratified on DAOH over the 120 days prior to randomization to either the intervention or control arms. The investigators will enroll patients for 10 months, accruing approximately 5000 patients. On an intention-to-treat basis, two groups of 2,500 patients would provide 80% power to detect an effect size of 0.08 standard deviations (SD) on our primary outcome, DAOH, assuming a two-sample t-test and a two-sided 0.05 significance level. Assuming that only 25% of intervention patients contacted actually enroll in the complex care management program, this study would be adequately powered to detect an effect size as small as 0.32 SDs on the primary outcome.

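### Poisson regression is named for every between-arm comparison without a variance estimator; with the model's own standard errors the expenditure test is invalid and the error rates for counts and DAOH are not assured

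*SAP*

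**What the plan says.** Under Analysis plan, the SAP states: "The investigators will compare the outcomes between the intervention and control arms with Poisson regression using arm assignment as the primary model term". The next sentence adds only the covariates: "Regressions will control for age, sex, race/ethnicity, and each prior baseline outcome". No outcome is exempted. The same model therefore covers quantities of different kinds:

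- the primary outcome, "Days alive and out of hospital (DAOH) at 120 days from randomization", which is bounded between 0 and 120;
- a money amount, "Total healthcare expenditures at 10 months from randomization";
- event counts, "All-cause hospitalizations at 10 months from randomization" and "All-cause emergency department visits at 10 months from randomization";
- mortality, which is binary.

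The SAP mentions no robust variance, dispersion term, negative binomial alternative or outcome-specific model. Under Power, the sample size is justified "assuming a two-sample t-test and a two-sided 0.05 significance level". The design is a "1:1 randomization stratified on DAOH over the 120 days prior to randomization" with 2,500 patients per arm. No mean, SD or dispersion is given for any outcome.

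**The concern.** A Poisson regression has two parts: a log-linear model for the mean, and the assumption that the variance equals the mean. With a robust variance, the first part can be used for all of these outcomes. The second part drives the default standard errors, and it has no reason to hold for dollars, for repeat admissions, or for a bounded day count that piles up near its maximum.

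If the default is used, the test no longer reflects the observed spread of the data. For expenditures, the quantity that the enrolling model predicts, a difference would be declared almost every time even with no effect. For the primary outcome, the test could reject too often or too rarely. The t-test behind the power statement uses the observed SD, so its alpha and power do not describe a Poisson test with default errors.

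**Working it through.** **1. The SAP's own figure.** Inputs from Power: 2,500 per arm, 0.08 SD, two-sided 0.05, two-sample t-test.

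Noncentrality = 0.08 / sqrt(2/2500) = 2.828. Power = Phi(2.828 − 1.96) = 0.807. The stated 80% reproduces, for a test that uses the observed SD.

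**2. Unit dependence of the expenditure test (no distribution assumed).** Dividing the outcome by c leaves the arm coefficient unchanged and multiplies its model-based standard error by sqrt(c). From dollars to thousands, c = 1,000, so z shrinks by sqrt(1000) = 31.6. In one simulated skewed-cost dataset with no arm effect, the coefficient was −0.0589 in both units. The model-based z was −252.7 in dollars and −8.0 in thousands. The sandwich (HC1) z was −0.87 in both.

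**3. Size of a nominal 5% test with model-based errors.** Let phi = residual variance / mean, with residual SD = SD × sqrt(1 − R²). In large samples:

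size = 2 × (1 − Phi(1.96 / sqrt(phi)))

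The size is 5% only when phi = 1. All means, SDs and R² below are assumptions, because the SAP gives none.

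*Expenditures*, mean $20,000 to $60,000, SD/mean 0.75 to 2, R² 0 to 50%:

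- Smallest phi in dollars: 20,000 × 0.75² × 0.5 = 5,625, size 98%. In thousands: 5.625, size 41%.
- Largest phi in dollars: 60,000 × 2² = 240,000, size 99.7%. In thousands: 240, size 90%.

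*Hospitalizations and emergency visits:* phi 1.5 gives 11%, phi 2 gives 17%, phi 3 gives 26%.

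*Mortality:* phi = 1 − p, so at p = 0.10 the size is 3.9%, mildly conservative.

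*DAOH at 120 days:* the break-even is residual SD = sqrt(mean), which is sqrt(110) = 10.49 days at a mean of 110.

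| Mean / SD (days) | R² | Size |
|---|---|---|
| 115 / 8 | 0 | 0.9% |
| 115 / 10 | 0 | 3.6% |
| 115 / 15 | 0 | 16% |
| 110 / 20 | 0 | 30% |
| 110 / 20 | 20% | 25% |
| 110 / 20 | 30% | 22% |

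Power for 0.08 SD at 115/8 = 1 − Phi(1.96 × sqrt(115)/8 − 2.828) = 1 − Phi(2.627 − 2.828) = 58%, against the planned 80%.

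**4. Simulation check.** Each scenario had 2,000 null trials of 5,000 patients, 1:1 allocation within month and stratum, and a Poisson fit with arm, age, sex, race/ethnicity and the prior value of the outcome (log scale for cost). Monte Carlo SE is about 0.5 points at 5% and 1 point at 25%.

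| Outcome (assumed) | Model-based | Sandwich (HC1) |
|---|---|---|
| Expenditures, mean $38,800, SD $55,900, R² 19%, in dollars | 99.4% | 4.4% |
| Same, in thousands | 79.5% | 4.7% |
| Hospitalizations, mean 0.8, phi 2.6 | 23.7% | 5.3% |
| DAOH, mean 113, SD 18 | 25.6% | 4.7% |
| DAOH, mean 117, SD 11.6 | 6.2% | 4.8% |
| DAOH, mean 118, SD 6.8 | 0.1% | 4.5% |

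The DAOH scenarios were built from assumed death/hospitalization rates of 6%/30%, 2%/20% and 0.3%/15%. Covariates explained under 1% of DAOH variance there, which is why step 3 also shows 20 to 30%. Separate null simulations under other assumptions gave 99.8% (dollars), 84% (thousands), 21% (hospitalizations) and 15% (DAOH) with model-based errors, against about 5 to 7% with HC1.

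**The case against.** The strongest reply is that the SAP is silent rather than wrong. It never says that model-based errors will be used, the investigators may intend robust ones, and the unseen protocol might say so. That is fair as to intent, and every consequence above is conditional on the default. It does not remove the point. The SAP is where the variance estimator belongs, and the method followed literally gives an invalid expenditure test. Silence also leaves the choice open until results are seen.

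Second, no error is demonstrated for the primary outcome. The scenarios run from 0.1% to 25.6%, one of them is close to nominal, and adjustment for prior DAOH helps: if covariates explained 20 to 30% of variance, the break-even total SD at a mean of 110 would rise from 10.5 to about 11.7 to 12.5 days (10.49/sqrt(0.8) and 10.49/sqrt(0.7)). This stands. The DAOH figures are illustrative, and the claim is only that the error rate is not assured.

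Third, planning an adjusted analysis with a t-test is a common simplification, and the SAP labels it as such. Agreed: it is not a separate defect, and it becomes a reasonable approximation once the variance is robust.

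Finally, the harm that needs no distributional assumption concerns a secondary outcome, the SAP states no error rate for secondary outcomes, and mortality would err slightly on the conservative side. These facts limit the weight of the point but do not answer it.

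**Conclusion.** The concern holds and should be fixed. That the variance estimator is unspecified, and that the expenditure p-value depends on the currency unit under default errors, is certain and rests on no assumed distribution. The sizes rest on assumed means, SDs and dispersions: near-certain false rejection for expenditures in dollars, roughly two- to fivefold inflation for counts at variance-to-mean ratios of 1.5 to 3, and for DAOH anything from well under 5% with lost power to about 30%. For the primary outcome the direction cannot be determined from the SAP. The Poisson mean model and the covariates are not at fault.

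**What to change.** Keep the log-link Poisson mean model and the planned covariates. Add one sentence under Analysis plan: all between-arm confidence intervals and p-values from these models use Huber-White (sandwich) standard errors, which for mortality is the modified Poisson approach. Point estimates do not change, the expenditure result no longer depends on the unit of money, and the t-test power figure becomes a reasonable approximation for the planned test. The cost is one sentence and one software option, with no new data or patients.

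### The between-arm regressions omit month of randomization, although patients are randomized in ten monthly batches: no bias, but a small and inexpensive gain in precision is left unused

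*SAP*

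**What the plan says.** The Power section sets out accrual and allocation: "The cost prediction model will identify approximately 500 patients each month, who will undergo a 1:1 randomization stratified on DAOH over the 120 days prior". It then gives the total: "The investigators will enroll patients for 10 months, accruing approximately 5000 patients". On the natural reading, each month's list is allocated 1:1 as its own batch, which gives ten batches.

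The Analysis plan section gives one model for the between-arm comparisons: "The investigators will compare the outcomes between the intervention and control arms with Poisson regression using arm assignment as the primary model term". It then lists the other terms: "Regressions will control for age, sex, race/ethnicity, and each prior baseline outcome". For the primary outcome, the "model will control for DAOH in the 120 days prior to randomization". No term for month, cohort or calendar time appears, and no variance estimator is named.

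The monthly cohort does appear as a unit once, under Exploratory Outcomes, in the assessment of the cost prediction model: "Observed healthcare expenditures for each month's control cohort will be measured over the subsequent 12 months after randomization". That analysis uses controls only and is not a between-arm comparison.

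**The concern.** When allocation is done within groups, the usual practice is to analyse by those groups. The design has already balanced the arms on them, and only an analysis that contains them takes credit for that balance. The SAP does this for prior DAOH, which is both the stratification factor and a covariate. It does not do it for month.

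Month may be prognostic. Enrolment over 10 months must cross seasons, so the 120-day follow-up windows of different batches fall at different times of year, and hospital use may differ between them. If so, variation between batches stays in the residual.

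Precision is at stake, not validity. It has some value here because the design has little to spare: it aims at 80% power for 0.08 SD, with 2,500 per arm against a requirement of 2,453.

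**Working it through.** **Inputs.** From the SAP: about 500 patients a month, 10 months, 2,500 per arm, 0.08 SD, two-sided 0.05, 80% power, two-sample t-test. Assumed: the share r of outcome variance that lies between months. The SAP gives no figure. The working range is 0.5% to 3%, with 5% and 10% shown as extremes.

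**1. The plan's own figure.** In SD units, the standard error of the difference is √(2/2500) = 0.02828. Power = Φ(0.08/0.02828 − 1.96) = Φ(0.868) = 80.7%. The required size is 2,453 per arm. The stated 80% is reproduced.

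**2. Interval width when the variance estimate reflects residual dispersion.** With arms balanced within month, the true standard error is proportional to √(1 − r). Without a month term, the reported one stays proportional to 1. The interval is therefore too wide by 1/√(1 − r) − 1:
- r = 0.5%: 1/0.9975 − 1 = 0.25%
- r = 3%: 1/0.9849 − 1 = 1.5%

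**3. Power for 0.08 SD and type I error, on the SAP's t-test scale.** With s = √(1 − r):
- power with month = Φ(0.08/(0.02828·s) − 1.96)
- power without month, exact 1:1 within month = Φ((0.08/0.02828 − 1.96)/s)
- type I error without month = 2[1 − Φ(1.96/s)]

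| r | Power with month | Power without month | Type I error without month |
|---|---|---|---|
| 0.5% | 80.9% | 80.8% | 0.049 |
| 1% | 81.1% | 80.9% | 0.049 |
| 2% | 81.5% | 81.0% | 0.048 |
| 3% | 81.9% | 81.1% | 0.047 |
| 5% | 82.7% | 81.4% | 0.044 |
| 10% | 84.6% | 82.0% | 0.039 |

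Across the working range the gain is about 0.1 to 0.8 percentage points.

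If the split within a month is left to chance, the test without month keeps its nominal size and has 80.7% power. The gain at r = 3% is then 81.9 − 80.7 = 1.2 points. In that case the number allocated to one arm in a month has SD √(500 × 0.25) ≈ 11 around 250.

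**4. Other covariates.** If prior DAOH explains a share R² of the variance, and month's contribution is separate from it, r is replaced by r/(1 − R²). As an illustration, a correlation of 0.4 gives R² = 0.16. At r = 3% the residual share is 0.03/0.84 = 3.6%, and the interval is 1.8% too wide rather than 1.5%.

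**5. The Poisson model as written.** Leave the other covariates aside and take equal arms within each month. Let M_k be the total outcome count in month k, M the sum of the M_k, and p the intervention arm's share of M. With month terms, the information on the log rate ratio is Σ M_k·p(1 − p) = M·p(1 − p). Without them it is also M·p(1 − p). The estimate and the model-based standard error are therefore identical.

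Poisson simulations agree. The ratio of model-based standard errors with and without month was 1.0000. With no other covariates and a month share of 1.3%, the robust standard error fell by 0.6% to 0.7% when month was added; 1 − √(1 − 0.013) = 0.65%. In a further Poisson simulation the robust standard error fell by 0.7%, 2.6% and 5% at month shares of 0.6%, 2% and 4%. Those falls exceed 1 − √(1 − r). They match step 4 with R² of about 0.6: at 2%, 1 − √(1 − 0.02/0.4) = 2.5%.

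**6. Bias.** In a linear simulation (10 batches of 500, 1:1 within batch, seasonal shifts in baseline and outcome, 2,000 runs per setting), a true effect of 0.08 was estimated at about 0.080 to 0.081 both with and without month.

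**The case against.** The strongest objection is that the formula in step 2 belongs to a linear model, while the SAP specifies Poisson regression and names no robust or quasi-Poisson variance. This stands. A reader might infer that the intervals, as the SAP is written, are wider than the design delivers. Step 5 shows that model-based Poisson standard errors do not respond to month at all. The gain exists only with a variance estimate that reflects residual dispersion, so the fix must include one.

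It is also fair to say that the effect is very small, that prior DAOH is the only stratification factor the SAP names, and that leaving month out is a permissible choice. All of this limits the priority of the point. It does not remove the case for adding a term that costs almost nothing.

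Three stronger inferences are tempting and are not supported:
- **Season biases the comparison or spoils the baseline adjustment.** The two 120-day windows span 240 days, so a patient's baseline and outcome periods share no days of the year. In the linear simulation, leaving month out moved the baseline slope from 0.40 to 0.39 (r = 1%) or 0.35 (r = 5%). But both arms in a month have the same windows, the slope is a nuisance parameter, and the arm estimate did not move. A slope that varies by cohort is not needed.
- **Early batches take a pool of high-cost patients that later batches exhaust.** The SAP describes no ranking or depletion of this kind.
- **An uneven split in some months confounds arm with season.** Under randomization this is chance noise, not systematic bias. A month term protects against it.

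**Conclusion.** The point holds as a minor one. The SAP allocates patients within monthly batches and leaves the batch out of its stated list of model terms. The arm comparison stays unbiased, and no conclusion of the trial is put in doubt. With robust or quasi-Poisson standard errors, intervals are about 0.25% to 1.5% too wide if month explains 0.5% to 3% of outcome variance, and somewhat more if prior DAOH explains part of the rest. With ordinary Poisson standard errors nothing changes.

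This rests on three assumptions: the between-month share, which the SAP does not give; the reading that each monthly list is randomized 1:1 as a batch; and, for the power figures, the SAP's own t-test scale.

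**What to change.** In the Analysis plan section, add month of randomization (10 levels, fixed effects) to the terms of every between-arm regression, and state that robust standard errors will be reported so that the gain is realised. This is about one sentence of SAP text. It uses 9 degrees of freedom out of about 5,000 patients, needs no new data because month is known for everyone, and does not affect the sample size. Writing it in now also avoids a later, post hoc decision about calendar adjustment.

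### Prior 120-day DAOH, the stratification factor, is adjusted for only in the primary model; adding it to the other between-arm models, with robust standard errors, is a small gain in calibration at no data cost

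*SAP*

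**What the plan says.** Under Power, the SAP describes a "1:1 randomization stratified on DAOH over the 120 days prior to randomization". Under Analysis plan, it will "compare the outcomes between the intervention and control arms with Poisson regression using arm assignment as the primary model term", and it gives one covariate rule for all of these models: "Regressions will control for age, sex, race/ethnicity, and each prior baseline outcome". The only worked example is that "for the DAOH-120 primary outcome, model will control for DAOH in the 120 days prior to randomization".

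Eight secondary outcomes are listed. Three are DAOH over other periods (30 days, 90 days and, for instance, "Days alive and out of hospital (DAOH) at 10 months from randomization"). The other five are expenditures, hospitalizations, emergency department visits, "All-cause mortality at 10 months from randomization" and "Ambulatory contact days out of home". Two exploratory outcomes, avoidable hospitalizations and avoidable emergency department visits, would also be compared between arms. The SAP does not say which standard error goes with the Poisson models.

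**The concern.** A variable used to balance the arms is normally carried into the analysis. Stratifying on a prognostic variable reduces the true sampling error of the arm comparison. A robust standard error from a model without that variable does not reflect the reduction, so it is somewhat too wide and the test somewhat conservative. Here the stratifier reaches the primary model only because it happens to be that outcome's own prior value. No sentence brings it into any other model.

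The rule also cannot be carried out for mortality. Every randomized patient was alive beforehand, so the prior value is a constant, and the SAP names no substitute. At stake is a little power, and correctly calibrated standard errors, in the secondary and exploratory comparisons.

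**Working it through.** **1. The rule set beside the outcomes**

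| Model | Own prior value under the rule | Prior 120-day DAOH in the model? |
|---|---|---|
| DAOH-120 (primary) | prior 120-day DAOH | yes |
| DAOH-30, DAOH-90, DAOH-10 months | prior DAOH over 30 days, 90 days, 10 months, if look-back matches follow-up | no, but an overlapping window |
| Expenditures, hospitalizations, ED visits, ambulatory contact days | own prior value | no |
| Mortality | constant, drops out | no; age, sex, race/ethnicity remain |

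If days in hospital follow an assumed first-order autoregressive daily process (day-to-day correlation 0.8 to 0.95), prior 120-day DAOH correlates 0.51–0.58 with the prior 30-day value, 0.88–0.93 with the 90-day value and 0.63–0.65 with the 10-month value. Less is therefore left to gain in those three models, least of all in DAOH-90.

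**2. The plan's own power figure**

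From the Power section: 2,500 per arm, 0.08 SD, two-sided 0.05. The standardized effect is 0.08/√(2/2500) = 0.08/0.02828 = 2.828. Power = Φ(2.828 − 1.960) = Φ(0.868) = 80.7%, which reproduces the stated 80%. Also 0.08/0.25 = 0.32 SD, as stated.

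**3. The same design as a yardstick for a secondary outcome**

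The SAP gives no R². Assume that prior 120-day DAOH explains a share R² of the variance beyond the planned covariates, that stratification balances it fully, and that standard errors are robust. Put s = √(1 − R²).

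- Stratifier omitted: type I error = 2[1 − Φ(1.960/s)]; power = Φ((2.828 − 1.960)/s).
- Stratifier included: type I error 5%; power = Φ(2.828/s − 1.960).

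| Assumed R² | s | Type I error, omitted | Power, omitted | Power, included | Gain (points) |
|---|---|---|---|---|---|
| 0.01 | 0.9950 | 4.9% | 80.9% | 81.1% | 0.3 |
| 0.05 | 0.9747 | 4.4% | 81.4% | 82.7% | 1.3 |
| 0.10 | 0.9487 | 3.9% | 82.0% | 84.6% | 2.6 |

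Gains are taken before rounding. The right comparator is the stratified trial analysed without the covariate, not the unstratified 80.7%. Using 80.7% would overstate the last gain as about 4 points.

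**4. Simulation of hospitalization-type counts**

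All inputs are assumed except the size and allocation: 5,000 patients in ten monthly cohorts of 500, randomized 1:1 within five categories of prior hospital days; mean count about 0.8; 3,000 replicates (Monte Carlo error about 0.4 points on type I error and 0.9 on power). The outcome's own prior count is in every model, as the SAP requires, and the stratifier is entered linearly. The direct effect of log(1 + prior hospital days) on the log rate is 0, 0.15 or 0.30. Power is at a log rate ratio of −0.1. Each cell reads without → with the stratifier.

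| Direct effect | Robust SE | Cut | Empirical SD | Type I error, robust | Power, robust | Model-based SE | Type I error, model-based |
|---|---|---|---|---|---|---|---|
| 0 | 0.0376 → 0.0375 | 0.3% | 0.0376 → 0.0376 | 4.9 → 5.1% | 74.9 → 75.1% | 0.0317 → 0.0317 | 9.8 → 9.9% |
| 0.15 | 0.0388 → 0.0383 | 1.3% | 0.0382 → 0.0383 | 4.5 → 4.9% | 70.9 → 72.0% | 0.0319 → 0.0319 | 10.4 → 9.9% |
| 0.30 | 0.0414 → 0.0403 | 2.7% | 0.0404 → 0.0404 | 4.3 → 5.0% | 64.4 → 67.1% | 0.0322 → 0.0322 | 12.0 → 11.8% |

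The empirical SD does not move. What improves is the match between the reported and the true error. The model-based standard error ignores the stratifier altogether and is too small whether or not it is included.

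Other assumed settings agree in order of size. Ten strata with stronger covariate effects gave cuts of 1.5% (0.0402 → 0.0396) and 3.1% (0.0415 → 0.0402), with 0.8 and 2.2 points of power. A simpler model without the own prior count gave 0.2% and 1.4%, with no visible change in power.

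**5. Mortality, assumed risk about 8%, no prior value in the model**

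Power is at a log odds ratio of −0.25, in the same three scenarios as step 4.

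| Direct effect | Robust SE: demographics / linear / log form | Power: demographics / linear / log form |
|---|---|---|
| 0 | 0.0955 / 0.0954 / 0.0953 | 60.1 / 60.2 / 60.3% |
| 0.15 | 0.0962 / 0.0958 / 0.0951 | 59.1 / 59.4 / 59.9% |
| 0.30 | 0.0990 / 0.0988 / 0.0968 | 52.5 / 52.7 / 54.2% |

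Linear entry cuts the standard error by 0.1–0.4% and log(1 + prior hospital days) by 0.2–2.2%. A simpler simulation with linear entry gave at most 0.8% (0.0857 → 0.0850).

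**The case against.** The strongest reply is that nothing here is an error. Adjusting each outcome for its own baseline is an accepted choice, the omission is conservative, and a mortality model with demographics alone is valid. All of that stands, and it is why this is a refinement only.

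It can also be said that the phrase about prior baseline outcomes might mean all of them in every model, in which case none would lack the stratifier. The SAP's example, which pairs one outcome with its own look-back window, argues against that reading. That the sentence allows both readings is a reason to clarify it.

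The objections on size also hold. The estimate gains no precision; the top figures need the strongest assumed effects; linear entry gives mortality only 0.1 to 0.3 points of power; and none of the simulations covers the three DAOH outcomes, expenditures or ambulatory contact days.

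Finally, the choice of variance estimator is a separate matter: the model-based type I error of about 10–12% is there with or without the stratifier and lends this point no weight. The two still need to be stated together, because with model-based errors the added covariate changes nothing.

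**Conclusion.** The point holds as a minor improvement. The design's stratifier is missing from the five non-DAOH secondary models and from the two exploratory avoidable-use models, and is present only through overlapping windows in the other three DAOH models. The mortality rule asks for a term that cannot be estimated. Under assumed inputs and robust standard errors, including the stratifier lowers the reported standard error by about 0.3–2.7% for hospitalization-type counts (0.2 to 2.7 points of power) and by under 0.5% for mortality with linear entry (0.8% at most in the simpler run). The SAP offers no R² by which to choose within these ranges.

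A reader might infer more, and the document does not support it:

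- that the secondary comparisons are biased or too liberal because of the omission. Randomization removes bias, and the omission errs on the conservative side.
- that the primary model is affected. It already contains prior 120-day DAOH.
- that mortality is analysed without adjustment. Age, sex and race/ethnicity stay in.
- that adjustment is worth several hundred patients. That figure credits the covariate with what stratification has already delivered.

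**What to change.** State in the Analysis plan:

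> *Every between-arm outcome model, including avoidable hospitalizations and avoidable emergency department visits, will include arm, age, sex, race/ethnicity, the outcome's own prior value where one exists, and prior 120-day DAOH in the form [stated here]. In the primary model prior 120-day DAOH is the planned covariate and enters once. All-cause mortality has no prior value; prior 120-day DAOH takes its place. All Poisson models will use robust (sandwich) standard errors.*

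The form should be fixed before outcomes are seen, for example log(1 + prior hospital days) or the randomization strata. Since everyone was alive throughout the look-back, prior hospital days are 120 minus prior DAOH. The choice of form matters most for mortality, where linear entry recovers almost nothing.

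The cost is SAP wording and one term in each of ten models (eight secondary, two exploratory). The variable is already held for every patient because randomization needs it. In DAOH-90 it will correlate strongly with the own prior value, which does not harm the arm estimate.

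Robust errors should be adopted knowingly. For overdispersed counts they are wider than default Poisson output (0.0383 against 0.0319 in the middle scenario with the stratifier), and that is the price of a type I error near 5%. For a binary outcome such as death they can be narrower (0.0857 against 0.0911 in the simpler simulation).

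### The between-arm regressions leave out model-predicted expenditure, a baseline score already held for both arms, and so give up a small amount of precision that would cost nothing

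*SAP*

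**What the plan says.** The Analysis plan section of the SAP compares the arms by Poisson regression, with arm as the main term, and lists the adjustment variables: "Regressions will control for age, sex, race/ethnicity, and each prior baseline outcome". No other covariate and no interaction is named.

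The Power section describes how patients enter: "The cost prediction model will identify approximately 500 patients each month, who will undergo a 1:1 randomization". Allocation is a "1:1 randomization stratified on DAOH over the 120 days prior to randomization". Predicted cost is therefore the route into the trial but is not a stratification factor.

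The score is used as an analysis variable in one place only. Under Exploratory Outcomes, predicted expenditure is compared with observed 12-month expenditure in the control arm and summarised by the area under the ROC curve.

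**The concern.** A score designed to forecast healthcare spending is a natural prognostic covariate for expenditures, hospitalizations, emergency visits, mortality and, less directly, DAOH. It is fixed before randomization. The SAP already plans to use it in the control arm, so adjusting for it needs no new data collection.

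The existing adjustment is also uneven across outcomes. For most of them, the prior value carries much of the prognostic information. For all-cause mortality at 10 months there is no usable prior value, because everyone is alive at randomization, so that model adjusts for age, sex and race/ethnicity alone. For total expenditures, the score forecasts the outcome itself.

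At stake is the width of the intervals, not their validity. It deserves some attention because the intention-to-treat effect the trial is sized for is small, at 0.08 SD.

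**Working it through.** **Inputs from the SAP, Power section.** 2,500 patients per arm, 5,000 in total; effect 0.08 SD; 80% power; two-sided 0.05; two-sample t-test.

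**Input assumed.** The extra share of outcome variance that predicted expenditure explains beyond the listed covariates, written R². The documents do not give it. A range of 0.01 to 0.10 is shown.

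**Step 1: the plan's own figure.** The SE of a difference in means, in SD units, is √(2/2500) = 0.02828. Then 0.08/0.02828 = 2.828, and power = Φ(2.828 − 1.960) = 0.807. The effect detectable with 80% power is (1.960 + 0.842) × 0.02828 = 0.0792 SD. The required size is 2,453 per arm, against 2,500 planned. The stated power reproduces. It rests on an unadjusted t-test and claims nothing from covariates, so omitting the score does not affect it.

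**Step 2: effect of adding the score.** The residual SD is multiplied by √(1 − R²), and interval width shrinks by the same factor. The equivalent number of extra patients is 5000/(1 − R²) − 5000. The residual SD before adding the score is set to 1; the proportional change does not depend on that choice. This is a linear-model approximation, in line with the SAP's own power statement, although the planned model is Poisson.

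| Assumed R² | Width factor | Narrowing | Equivalent extra patients | Detectable effect (SD) | Power at 0.08 SD |
|---|---|---|---|---|---|
| 0 | 1.000 | 0 | 0 | 0.0792 | 0.8074 |
| 0.01 | 0.995 | 0.5% | 51 | 0.0788 | 0.8113 |
| 0.02 | 0.990 | 1.0% | 102 | 0.0784 | 0.8152 |
| 0.05 | 0.975 | 2.5% | 263 | 0.0772 | 0.8269 |
| 0.10 | 0.949 | 5.1% | 556 | 0.0752 | 0.8465 |

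**Step 3: where in the range.** For DAOH the low end is the more likely. The model already contains prior DAOH, randomization is stratified on it, and selecting patients by the score probably narrows the score's range within the trial.

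**Step 4: an arm-by-score term.** With the score in SD units among enrolled patients and unit residual SD, the SE of the difference in slopes is 2/√5000 = 0.0283. The 95% half-width is 1.96 × 0.0283 = 0.055 SD per SD of score, which is 0.055/0.08 = 69% of the design effect. The slope difference detectable with 80% power is 2.80 × 0.0283 = 0.079, so the effect would have to change by about its whole design size for each SD of score.

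**The case against.** The strongest reply is that nothing in the SAP is wrong here. Demographics plus the prior value of the outcome is a valid prespecified adjustment set. Omitting a further prognostic variable in a 1:1 randomized trial introduces no bias, the power figure stands, and the precision gain rests on an R² that the documents do not supply and that could be close to zero for DAOH. All of that is correct. It limits the size of the point but does not remove it, because the variable is already available and adjusting for it takes one model term.

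A reader might go further and infer that, with no term linking the score to treatment effect, the trial cannot evaluate the model, or that its result says nothing about using the model for enrolment. The title, "Evaluation of AI Cost Prediction Model to Enroll Patients in Complex Care Management Program", invites that reading, but the document does not support it. Randomizing flagged patients to program or control directly tests whether offering the program to those patients improves outcomes. The SAP states no aim of ranking patients by benefit within the flagged group. Since the score exists in both arms, the design would also permit such an analysis; the plan simply does not include it.

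Nor would an interaction term settle whether the model selects better than another rule, because patients who are not flagged are not randomized. It would also be imprecise: the SAP assumes that only 25% of contacted intervention patients enroll, which dilutes intention-to-treat effects and any differences between them. What does stand is narrower: the control-arm ROC analysis measures prediction of cost, and no planned analysis relates the score to benefit.

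**Conclusion.** The point holds as a modest improvement to the covariate list. It is not an error or a contradiction in the plan. Under an assumed incremental R² of 1% to 10%, adding predicted expenditure narrows intervals by about 0.5% to 5%, and the DAOH gain probably lies near the bottom of that range. At R² of 0.02, for example, power at 0.08 SD moves only from 0.807 to 0.815. Total expenditures and mortality have the better claim, though the documents allow no figure specific to either. The conclusion assumes that a numeric prediction at randomization is retained for patients in both arms. This follows from how they are selected, but the SAP does not say so outright.

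The missing arm-by-score term is not a defect. Including one is a reasonable option if it is presented as an exploratory description of flagged patients.

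**What to change.** In the Analysis plan section, add model-predicted expenditure at randomization, on the log scale or as a spline, to the covariates of every between-arm regression. State that the value used is the one generated before randomization.

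Optionally, prespecify one arm-by-predicted-expenditure term for DAOH at 120 days and for total expenditures. Label it exploratory, report it as an estimate with a confidence interval, and note that it applies to flagged patients only and does not compare the model with other selection rules.

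The cost is a change of wording, one extra model term and, if the option is taken, one extra exploratory estimate for each of the two outcomes. No additional patients or data are needed. The wording should be settled before any comparison between arms is seen; otherwise both additions would be post hoc.
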